**Toward Understanding Drivers of Patient Engagement With Digital
Mental Health Interventions – Part I**

NCT05360901

Date: 9/28/2023

Institutional Review Board Intervention/Interaction Detailed Protocol

Principal Investigator:	[name]
Project Title:	Toward Optimizing Digital Mental Health Interventions: A Clinical Trial Aimed at Understanding What Drives Patient Engagement – Part 1
Version Date:	National Institute of Mental Health
Version Name/Number:	9/28/23

1. Background and Significance

Digital mental health interventions (DMHIs), delivered via the internet and/or mobile apps, have the potential to remove many of the barriers that plague in-person behavioral health interventions. They can be widely disseminated at minimal marginal cost, do not require transportation or daytime appointments, and promote patient autonomy. Reviews and meta-analyses suggest that DMHIs are effective in controlled research settings.¹⁻³ But, in routine care implementations, effectiveness is limited by insufficient engagement.^{4,5} Only 20-50% of patients engage at the recommended frequency and/or complete the full course of treatment.^{4,6,7} The strongest hypothesis to date is that achieving reliable engagement with DMHIs requires adding human support.^{8,9} But strategies for adding human support are widely varied—from less scalable options like weekly phone calls with a clinician to more scalable options such as asynchronous communication with a health coach—and little is known about the impact of the more scalable strategies. A less explored, even more scalable strategy for improving engagement is automated motivational messaging (AMM). While AMM has been effective in some trials,^{10,11} little is known about what content or delivery characteristics drive its impact. Understanding whether fully automatized intervention components can improve engagement without human support, and what drives patient engagement in either condition will be essential. This study applies a patient-centered approach to developing the look, feel and written content for a set of AMMs that could be used to enhance patient engagement with DMHIs.

2. Specific Aims and Objectives

This study aims to systematically employ patient feedback to develop a set of automated motivational messages aimed at enhancing engagement with digital mental health interventions.

This study is a precursor to a subsequent full-scale clinical trial that will test the impact of digitally delivering these messages on patient engagement with a digital mental health intervention.

3. General Description of Study Design

This is an in situ user-centered design study for the automated motivational push messaging we are developing. Users will download an example DMHI (IntelliCare) use it for three weeks. In tandem, they will receive automated motivational push messages from the set that we have in development on a randomized schedule. That is, each day they will be randomized to either receive an automated motivational push message (60% likelihood) or not receive an automated motivational message (40% likelihood). On days when they receive a push message, they will then be prompted to complete a brief survey on their reaction to the push message. They will also be asked to complete weekly symptom ratings. At the end of three weeks, they will be asked to complete a qualitative interview to provide further feedback on messages under development.

The primary outcome in this study is user ratings from the brief surveys provided after push notification delivery. We will also, however, look at user feedback on messages under development in the qualitative interview as well as whether receiving a message makes users more likely to engage with the DMHI (IntelliCare) during the three hours following message delivery.

4. Subject Selection

We will enroll up to 40 patients with clinically significant anxiety and/or depression. Inclusion criteria will be: (i) Age 18+; (ii) Patient Health Questionnaire-8 (PHQ-8) score ≥ 10 and/or Generalized Anxiety Disorder-7 (GAD-7) score ≥ 8 ; (iii) owns a smartphone; (iv) fluent in English; and (v) have a MGB primary care provider. Exclusion criteria will include: (i) diagnosis of bipolar disorder, any psychotic disorder, or a current substance use disorder per patient's report or medical record; (ii) acute and/or unstable medical problem that may interfere with participation (e.g., scheduled for surgery in the next two months).

Thus, enrollment will be open to all English-speaking, adult, MGB primary care patients with clinically significant depression and/or anxiety and no current or past serious mental illness or acute medical illness that may interfere with participation. Potential subjects who do not speak English will be excluded from the study due to the fact that not all of the validated assessments used are available in languages aside from English. Additional eligibility criteria will be added as needed after recruitment of N=10 participants to ensure adequate representation of racial minorities and men (who are historically underrepresented in studies on depression and anxiety disorders).

Subjects will be recruited from the Mass General Brigham Clinical Trials website/Rally and RPDR patients who have not opted out of Research Invitations. We will send IRB-approved recruitment letters by mail and Patient Gateway messages. We will also recruit from ongoing studies across the MGB system being conducted by colleagues with IRB approval to offer current participants opportunities to participate in other ongoing research. An IRB-approved telephone script will be utilized by the study research assistant to pre-screen subjects prior to scheduling.

5. Subject Enrollment

An IRB-approved telephone script will be utilized to pre-screen subjects prior to scheduling.

Once a potential subject has been pre-screened, the study research assistant will review the consent form verbally with eligible subjects. Eligible subjects will be given an opportunity to ask questions by phone. Potential subjects are not required to sign the consent on-the-spot, they are able to carefully read the document and discuss the research with their family, friends and/or physician and develop questions to ask the research staff. Once they have read the consent document and their questions are answered by a qualified member of the study staff, if they agree to participate in the research, they will be provided a copy of the consent form via REDCap to sign.

Consented subjects will be scheduled for a study enrollment call via phone or Zoom based on the participants' preference. During this call, participants will be guided through the download process for the study intervention app (IntelliCare) and the push notification delivery/survey app (MyDataHelps and/or Catalyst by MetricWire) on their personal smartphone. Participants will be randomized each day over the next three weeks to either receive a push notification from the pool of notifications being tested (60% probability) or not (40% probability). Daily randomization will be done using the R package randomizeR.

6. Study Procedures

User-centered, participatory design consists of iterative qualitative feedback meetings with patients (i.e., participants). Up to 40 participants will be recruited for this study. After screening (by phone), eligible participants will be invited to participate in the study. After consent, but prior to enrollment, study staff will check diagnoses in participants' EPIC chart to ensure that participants do not meet exclusion criteria.

The first step in study participation will be for participants to complete an enrollment call and an enrollment survey in REDCap. The enrollment survey will include a demographic questionnaire, the Technology Adoption Propensity Scale, symptom surveys and a brief enrollment survey on messaging preferences. The enrollment call will be conducted via phone or Zoom (per the participant's preference) with study staff. The call will entail walking users through downloading the study intervention app (IntelliCare) and the push notification delivery/survey app (MyDataHelps and/or Catalyst by MetricWire) on their personal smartphone. Participants will be told that IntelliCare is most effective when used on a daily basis and be asked to respond to surveys attached to push notifications by tapping on the push notification. Participants will then be randomized each day to either receive a push notification from the pool of notifications being tested (60% probability) or no notification (40% probability). On days when a push notification is received, they will have the opportunity to respond to a brief survey in the MyDataHelps and/or Catalyst by MetricWire app on their reactions to the notification. Participants will earn \$2 for each push notification survey they complete. At the end of week 1 and week 2, participants will be prompted to complete a depression severity self-report measure (PHQ-8) and an anxiety severity self-report measure (GAD-7) and will earn \$5 each week these are completed.

Three weeks later, participants will be invited to engage in a study visit, either in lab or remotely via Zoom, based on current COVID-19 prevention guidelines and the participant's preference. Study visits will last up to 90 minutes and will involve meeting with one or two members of the study team.

In the study visit, participants will be given the opportunity to ask any questions they have about digital mental health interventions and/or the goal of the automated motivational messaging being developed. They will then be asked to complete a brief self-report questionnaire including the PHQ-8, GAD-7 and a repeat administration of the enrollment survey (to evaluate whether answers have changed). The remainder of the meeting will consist of a qualitative interview focused on generating subject feedback on design and content considerations in development of automated motivational messages. Subjects will be asked to offer additional feedback related to messages received over the preceding 3 weeks and be presented with low-fidelity prototypes of additional messages not delivered in the preceding 3 weeks with open-ended questioning used to generate feedback.

Participants will be paid \$50 for participation in the study visit. All meetings with participants will be audio recorded and recordings will be immediately transferred onto Partners secure servers and deleted from the recording device. All recording devices will be stored in the PI's lab in a locked file cabinet.

The primary outcome in this study is user ratings on message likeability and message motivation from the brief surveys provided after push notification delivery. We will also, however, look at user feedback on messages under development in the qualitative interview as well as whether receiving a message makes users more likely to engage with the DMHI (IntelliCare) during the three hours following message delivery.

The intervention offered as part of this study is only intended to facilitate user-centered design and will be presented as such. It will not be considered part of the participant's treatment plan nor will it be presented as an alternative to other treatment. Neither participation in this study nor engagement with the intervention app prohibit participants from engaging with other treatments for depression and/or anxiety. This study does not involve ongoing assessment of clinical symptoms because this is not an outcome consistent with study aims. If at any point, a participant expresses that participation in the study may be adversely impacting his or her mental health, study staff will make it clear to the participant that he or she can choose to withdraw at any time. Participants can be removed from the study at any time at their own request.

7. Risks and Discomforts

Foreseeable risks that might exist are described in the following four categories: (a) risks associated with the intervention; (b) risks associated with study visits; (c) risks associated with potential loss of confidentiality; and (d) risks of worsening mental or emotional state.

(a)Risks associated with the intervention: Technology-enabled mental health intervention programs have not been shown to cause any harm. The clinical risks of the intervention used in this study are very low. The digital mental health intervention being used in this study (IntelliCare) has been studied previously with no serious adverse events and potential for clinical benefit. The IntelliCare suite is already in public use. Participants may continue with or begin any other treatments they choose for anxiety and/or depression while they are engaging in the app-based intervention.

(b)Risks associated with study visits: Subjects may experience fatigue from the study visits, and potential discomfort from the nature of questions. Some of the questions asked in the qualitative

interview may be unsettling, but most will not be. Subjects may refuse to answer any questions that they do not want to answer. Additionally, subjects are allowed to take breaks throughout the study visit at their request. Risks involving the compromise of privacy and confidentiality during study visits will be minimized through the utilization of the PI's laboratory space, where there are private rooms for study visits and infrastructure in place to ensure the proper adherence to IRB-approved protocol such as the use of password protected computers and locked storage space.

(c) Risks associated with potential loss of confidentiality. As with all studies, potential loss of confidentiality is also a risk. Risks in this study are minimized by using secure online data collection tools –REDCap, the MyDataHelps and Catalyst by MetricWire are HIPAA compliant. The IntelliCare app can be used anonymously with participants labeled by a study ID number only. Additionally, questionnaire data collected has been limited to only those measures essential for addressing primary aims of this project. Still, there is some possibility that others may see the app open on the participant's smartphone. There is also the possibility that databases may be hacked. Confidentiality may be broken by research staff to ensure the patient's safety if there is an imminent threat to self or others. All of these potential losses of confidentiality will be disclosed in the consent documents.

(d)Risks of worsening mental or emotional state: It is not believed that the risk of these depressive, anxious, suicidal, or other adverse outcomes are increased as a function of being enrolled in this study. However, due to the common course of depression and anxiety, it is expected that there will be exacerbations in symptoms of some participants over the course of the study. Subjects may pursue all treatment services they otherwise would alongside participating in this study.

While there is no point in which we are assessing current suicidality, several procedures are in place to protect participants who convey suicidality in the course of their participation. Language in participants' free-form responses to questions in the intervention app (IntelliCare) are continuously monitored by the IntelliCare system. If any words related to death, suicidality or means of suicidality (e.g., gun, pills) are mentioned, the participant will receive an automated message indicating the following *"IntelliCare is NOT an emergency service. If you do not feel safe and need immediate police or medical assistance, call 9-1-1 or go directly to your nearest emergency room."* Additionally, the study PI (or covering clinician) would receive an alert and call the participant. Additionally, if at any time, a subject communicates any imminent safety risk, they will be assessed by the PI (a licensed psychologist) or a covering clinician and referred for immediate care if it is clinically determined.

8. Benefits

There may be no immediate benefits to you from participation in this research study; however, results may allow researchers to design effective ways to better engage patients with digital mental health interventions. Subjects engaged in this type of participatory design research, sometimes report a sense of accomplishment from participation.

9. Statistical Analysis

The primary aims of this study are qualitative and descriptive consistent with user-centered design standards. Descriptive data will be collected on the following: average likability ratings for messages sent, average motivation ratings for messages sent, percentage of the time users

engaged with the intervention app (IntelliCare) within three hours of receiving a message. Daily randomization of message delivery is being applied to mirror message frequency delivery to what we intend to use in the clinical trial not to infer causality.

Data from qualitative interviews will be analyzed using a rapid qualitative analysis approach.¹² Final decisions on messaging will be made in consultation with my mentorship team with the goal of producing 10-15 messages in each “bucket” (i.e., targeting attitude, self-efficacy and habit strength respectively) to avoid delivering redundant messages in the clinical trial.

10. Monitoring and Quality Assurance

As the proposed study involves no more than minimal risk to subjects, there is no formal Data Safety Monitoring Board established for this study. The PI will review safety data in real time to address any concerning adverse events and discuss these with her mentor, [name]. [name] has served as an active member of three IRBs over the past 15 years and will ensure that all AEs are appropriately reported and followed up.

The principal investigator will oversee the data collection and will ensure that any adverse events are recorded and properly reported. We do not anticipate frequent problems given that this is a minimal risk protocol; however, we will closely monitor data collected in the event of any unanticipated problems. In the event of any unanticipated problems and adverse events we will report to the PHRC: 1) during the conduct of the study, 2) after study completion, or 3) after subject withdrawal or completion. Reports are to be submitted within 5 working days/7 calendar days of the date the investigator first becomes aware of the problem, as outlined in Partners System-wide policy.

Self-report data will be collected in REDCap and the HIPAA-compliant MyDataHelps and/or Catalyst by MetricWire app. Additionally, de-identified participant engagement data will be collected automatically via the IntelliCare app. Assurance of data validity and integrity will be monitored closely by the PI. Similarly, audio recordings of subject interviews will be uploaded onto the research drive (and deleted from the recording device) the day the interview is conducted. The principal investigator will work closely with the rest of the study team to ensure the study is in adherence to the IRB-approved protocol.

11. Privacy and Confidentiality

- Study procedures will be conducted in a private setting
- Only data and/or specimens necessary for the conduct of the study will be collected
- Data collected (paper and/or electronic) will be maintained in a secure location with appropriate protections such as password protection, encryption, physical security measures (locked files/areas)
- Specimens collected will be maintained in a secure location with appropriate protections (e.g. locked storage spaces, laboratory areas)
- Data and specimens will only be shared with individuals who are members of the IRB-approved research team or approved for sharing as described in this IRB protocol
- Data and/or specimens requiring transportation from one location or electronic space to another will be transported only in a secure manner (e.g. encrypted files, password protection, using chain-of-custody procedures, etc.)

- All electronic communication with participants will comply with Mass General Brigham secure communication policies
- Identifiers will be coded or removed as soon as feasible and access to files linking identifiers with coded data or specimens will be limited to the minimal necessary members of the research team required to conduct the research
- All staff are trained on and will follow the Mass General Brigham policies and procedures for maintaining appropriate confidentiality of research data and specimens
- The PI will ensure that all staff implement and follow any Research Information Service Office (RISO) requirements for this research
- Additional privacy and/or confidentiality protections

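### At the final visit an optional, unscripted question period that may cover the purpose of the messages comes directly before the repeat enrollment survey, adding an avoidable influence to a before-after comparison

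*Combined protocol and SAP*

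**What the plan says.** Section 6 (Study Procedures) gives the final visit three steps in a fixed order.

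1. Questions: participants may "ask any questions they have about digital mental health interventions and/or the goal of the automated motivational messaging being developed".
2. Questionnaires: "They will then be asked to complete a brief self-report questionnaire including the PHQ-8, GAD-7 and a repeat administration of the enrollment survey". The stated purpose of the repeat is "to evaluate whether answers have changed".
3. Interview: "The remainder of the meeting will consist of a qualitative interview focused on generating subject feedback on design and content considerations".

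Earlier in Section 6, the baseline battery is described as including "a brief enrollment survey on messaging preferences", alongside demographics, a technology adoption scale and symptom surveys.

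Section 6 names the in-app likeability and motivation ratings as the primary outcome. Section 9 (Statistical Analysis) calls the primary aims qualitative and descriptive. It lists three descriptive quantities: average likability, average motivation, and how often users opened IntelliCare within three hours of a message. The repeat enrollment survey is not on that list.

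**The concern.** A question about whether answers have changed needs two measurements taken under comparable conditions, even when the answer is only descriptive. Here the second measurement directly follows a conversation with staff that may be about the very thing the survey asks about. A participant who asks what the messages are meant to do hears the team's rationale just before stating messaging preferences again. A participant who asks nothing does not. Any resulting shift, including a wish to agree with the team, enters the recorded change unevenly.

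What is at stake is how cleanly the repeat survey can be read. It is the only formal before-after comparison of messaging preferences in the study. Sections 7(c) and 11 say that questionnaires were limited to measures essential to the primary aims, so the protocol does not treat it as incidental.

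**Working it through.** The plan states no figure for this comparison, so there is nothing to reproduce. The check is a reading of the order of steps, plus two short calculations.

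**Order of steps.** In Section 6 the word introducing the questionnaires places them after the question period, and the interview takes up the rest of the meeting. So the question period can influence the survey, while the interview and the prototype messages cannot.

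**What is repeated.** The term enrollment survey is used both for the whole baseline battery and for the short part on messaging preferences. The PHQ-8 and GAD-7 are listed separately at the visit, which suggests that the short part is meant. Under either reading, messaging preferences are asked again. These are the items most open to influence from a talk about the messages; the symptom scales are less obviously so.

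**Standardisation.** Section 6 describes no script, time limit or topic record for the question period. It does say that all meetings are audio recorded.

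**Is there an unexposed comparison?** Inputs from Sections 3 and 6: three weeks, taken as 21 days, with a 60% chance of a message each day.

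- Expected messages per participant: 21 × 0.6 = 12.6
- SD: √(21 × 0.6 × 0.4) = √5.04 ≈ 2.2
- Chance of receiving none: 0.4^21 ≈ 4 × 10⁻⁹

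In effect every participant receives messages. The change from enrollment to visit therefore has no unexposed group to set against it, whichever order the visit follows.

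**Form of the bias.** Let p be the share of attendees who raise the messaging goal, and d the average shift in their answers caused by the reply. Then

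recorded mean change = change without the talk + p × d.

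The added term runs from 0 (nobody asks) to d (everybody asks). The documents give neither p nor d, so no size can be put on it. With the questionnaires first, this term is zero by design.

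**What is outside its reach.** The in-app ratings are collected on message days during the three weeks, and IntelliCare use is logged automatically over the same period. Both precede the visit.

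**The case against.** The strongest case on the other side has five parts.

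- **The talk is optional.** Participants have an opportunity to ask, and the messaging goal is one of two possible topics. A reader might infer that staff brief everyone on the goal; the text plans no such briefing. This stands, and it is why the influence is described as possible and uneven.
- **The order is not what prevents attribution.** A reader might infer that the visit order is the reason a change cannot be credited to three weeks of messages. The documents do not support that. There is no unexposed group, IntelliCare is used alongside the messages, other treatments are allowed, and the survey is a repeat. With the order reversed, attribution would still not be possible. This stands in full.
- **No attribution is planned.** The stated purpose is only to see whether answers changed, and Section 9 describes the aims as qualitative and descriptive. This stands, but it does not remove the point: a described change is still altered if the conditions of the second measurement differ. Section 9's statement that causality is not being inferred concerns the daily randomization, not this survey.
- **Baseline may also follow staff explanation.** Under Section 5 staff review the consent form verbally and answer questions before enrollment, and Section 6 does not show that the enrollment survey precedes all discussion. This stands in part. Those exchanges are also unstandardised, so they cannot be assumed to balance a conversation held just before the second survey.
- **Other evidence exists, and exposure can be recovered.** The in-app surveys and the interview also capture reactions to real use, and the audio recordings would show who asked about the goal. Both stand. The recordings would allow results to be described by who asked, but would not cleanly remove an effect, since those who ask may differ from those who do not.

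**Conclusion.** The point holds as a minor weakness in measurement. An optional, participant-led and unstandardised question period that may cover the messaging goal comes directly before the PHQ-8, GAD-7 and repeat enrollment survey. Staff answers could shift that second measurement by different amounts across participants, on top of a before-after comparison that is already uncontrolled.

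It can touch only attendees who raise the topic, out of at most 40 enrolled. The size of the shift cannot be derived from the documents. The conclusion rests on one assumption: that hearing the purpose of the messages can move stated messaging preferences. If it cannot, the order is harmless.

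It should not be read as a threat to the study's main results, because the primary ratings and the engagement data are complete before the visit.

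**What to change.** In Section 6, reverse the first two steps of the final visit. Participants complete the PHQ-8, GAD-7 and repeat enrollment survey first, for example in REDCap at the start of the visit, before any discussion. The question period and the interview follow. Whether questions come before or after the interview can be left to the team; the documents give no reason to require either.

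The cost is a small edit to Section 6 and to any visit checklist. Visit elements, staffing, duration and participants' opportunity to ask questions are unchanged. If the present order is kept, noting for each participant whether the messaging goal was raised would at least let the change be described with that in view.

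### Sections 3 and 6 ask whether a message raises IntelliCare use in the next three hours, but Section 9 plans only a message-day percentage with no no-message rate beside it

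*Combined protocol and SAP*

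**What the plan says.** Section 3 (General Description of Study Design) and Section 6 (Study Procedures) name the user ratings as the primary outcome. Both then add that the study will look at "whether receiving a message makes users more likely to engage with the DMHI (IntelliCare) during the three hours following message delivery".

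Section 9 (Statistical Analysis) calls the primary aims qualitative and descriptive and lists three summaries: mean likeability, mean motivation, and the percentage of the time users "engaged with the intervention app (IntelliCare) within three hours of receiving a message". It says the daily randomisation is there "to mirror message frequency delivery to what we intend to use in the clinical trial not to infer causality".

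Sections 3, 5 and 6 give the daily allocation: a message with probability 60%, none with probability 40%, over three weeks. Section 5 adds: "Daily randomization will be done using the R package randomizeR". Section 10 says that "de-identified participant engagement data will be collected automatically via the IntelliCare app".

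**The concern.** Saying that a message makes use more likely compares two rates: use after a message, and use over a like period without one. Section 9 plans only the first. A message-day percentage mixes any effect of the message with use that would have happened anyway. Such background use is plausible here, because Section 6 states: "Participants will be told that IntelliCare is most effective when used on a daily basis".

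Nor do the documents define a three-hour window on a day without a message, so the missing rate cannot be computed from the plan as written. Nothing says that no-message-day data are discarded; those days are simply absent from the planned summary.

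At stake is how the result is read. Someone who has read Sections 3 and 6 will expect a comparison and may take the message-day percentage as evidence of an effect.

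**Working it through.** **1. The texts side by side.** Sections 3 and 6 put a comparative question in causal wording. Section 9 gives a single-condition percentage and declines causal inference. No other section supplies a no-message rate, a contrast or a model. The documents give no sample-size derivation, expected use rate or power for this item, so there is no stated figure to reproduce.

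**2. What the message-day percentage leaves open.** Assume use within three hours on 30% of message days. The effect is the message-day rate minus the no-message rate:

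- no-message rate 0%: 30 - 0 = +30 points
- no-message rate 30%: 30 - 30 = 0 points
- no-message rate 40%: 30 - 40 = -10 points

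The planned output is 30% in all three cases.

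**3. Days available.** Inputs are up to 40 participants (Section 4), three weeks, and 60/40 allocation, with full follow-up and no missing days.

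- 40 × 21 = 840 user-days
- 840 × 0.6 = 504 with a message
- 840 × 0.4 = 336 without, which is 40% of the total and unused in Section 9

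**4. Precision if both rates were reported.** An approximate standard error for the within-user risk difference is

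SE = √[ p(1-p)(1-ICC)(1/N1 + 1/N0) + τ²/n ], with 95% half-width 1.96 × SE.

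N1 and N0 are message and no-message days, n is users, ICC is the within-user correlation and τ is the between-user SD of the effect. Assumed values, none of them in the documents: p = 0.3; low end ICC = 0.5 and τ = 0; high end ICC = 0.1 and τ = 0.10.

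At 40 users and 21 days, 1/504 + 1/336 = 0.00496.

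- Low end: 1.96 × √(0.21 × 0.5 × 0.00496) = 0.0447
- High end: 1.96 × √(0.21 × 0.9 × 0.00496 + 0.01/40) = 0.0675

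| Users × usable days | Message / no-message days | 95% half-width (points) |
|---|---|---|
| 40 × 21 | 504 / 336 | 4.5 to 6.8 |
| 20 × 21 | 252 / 168 | 6.3 to 9.6 |
| 20 × 15 | 180 / 120 | 7.5 to 11.0 |

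The first row is the best case for user and day counts; the lower counts are assumptions. Varying the use rate at the cap instead (p from 10% to 50%, ICC from 0 to 0.3, τ = 0) gives 3.5 to 6.9 points:

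- 1.96 × √(0.09 × 0.7 × 0.00496) = 0.035
- 1.96 × √(0.25 × 1.0 × 0.00496) = 0.069

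That is useful precision for an exploratory estimate. It does not make the study a powered test.

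**The case against.** The strongest reply is that the comparison was declined on purpose. Section 9 is the only analysis section; it calls the aims descriptive and says why the days are randomised. On that reading only a loosely worded sentence remains, repeated in two places, and adding a contrast would turn a design study into an effect analysis it never set out to be.

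Part of this stands. The disclaimer explains why no test is planned, and a sponsor who holds to it need only correct the wording. But it conflicts with the wording of Sections 3 and 6 and does not resolve it, so one side has to change. Nor does a descriptive purpose exclude a comparator: two percentages side by side are still descriptive.

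Three further points are fair.

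- The consequence is small. No decision rule uses the figure, and Section 2 says a later trial will test the messages' effect on engagement.
- The contrast would not be against a never-messaged baseline. Messages aimed at attitude, self-efficacy and habit may carry over into later days, so it measures that day's message given recent message history.
- Feasibility is not established. Section 10 refers to automatic collection and Sections 7 and 11 to "participants labeled by a study ID number only", which suggest usable logs. Neither time-stamping on all days nor linkage is stated.

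**Conclusion.** The concern holds. Followed exactly, the plan cannot answer a question it states twice. The mismatch rests on the text alone and is certain. The size of the resulting error cannot be known from the documents: under an assumed 30% message-day rate, effects from +30 to -10 points are all compatible with the planned result.

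This should be fixed, but its reach is limited. The likeability and motivation ratings and the choice of messages are unaffected. The 504/336 split assumes full enrolment and complete follow-up, and the half-widths rest on the assumed use rate, correlation and effect variation.

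**What to change.** Either of two changes reconciles the sections.

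**Option A: report the comparison.**

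1. When the daily randomisation list is made, assign every user-day a scheduled reference time by the same rule, whether or not a message is sent. Setting the rule before the logs are examined prevents choosing the window to suit the result.
2. Tabulate IntelliCare use in the three hours after that time on all randomised days.
3. Report both percentages and the within-user risk difference with a user-clustered 95% confidence interval, for example by GEE or by weighted and centred least squares using the known 0.6 probability.
4. Label the contrast exploratory, and as the effect of that day's message together with its paid survey prompt, given recent message history. The survey comes only with a message: Section 6 asks users to "respond to surveys attached to push notifications by tapping on the push notification" and pays $2 for each one completed.
5. Narrow the caveat in Section 9 to say that the contrast is exploratory and that the study is neither designed nor powered as a test of effect.

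The cost is a reference-time rule and one analysis paragraph, with no added participants, visits or questionnaires. It depends on logs that are time-stamped on all days and linkable by study ID, which should be confirmed beforehand. The documents give no delivery-time rule, so the programming effort cannot be judged from them.

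**Option B: keep the summary and change the aim.** Retain the message-day percentage and reword the sentence in Sections 3 and 6 as a description of use after a message, with no claim that the message causes it. The cost is two sentences. This suits a sponsor who wishes to keep the disclaimer as it stands.
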